8.4 Drug accountability

The Sponsor will supply the clinical Investigator with the investigational product, and other clinical drug supplies as agreed upon for the timely completion of the clinical study described above.

The investigational products (Nanocort and Depo-Medrol, as well as the placebo dummies) will be delivered to the study pharmacy. Study pharmacists will be unblind. It will be the responsibility of the study pharmacist to prepare the individual treatments based on randomization, treatment group and dose. Preparation on site is required to ensure the study blind. The investigational products will be dispensed only under the restricted conditions defined in the present protocol. Drugs will be administered by blinded personnel only. Time (start and end time of infusion) and date of administration and initials of the person administering the drug will be documented.

The pharmacist will record and acknowledge receipt of all shipments of the investigational product and document the lot numbers and condition of each shipment. The investigational products must be kept in a locked area with restricted access. The investigational products must be stored and handled in accordance with the manufacturer's instructions. The Investigator is responsible for maintaining documentation showing the amount of investigational product provided to the investigational site, and administered to and collected from each study patient. Discrepancies in investigational product accountability must be explained and documented. An inventory of investigational products will be maintained. The unblinded monitor will be responsible for verifying the Investigator's documentation on receipt, use and return of investigational products. The unblinded monitor will check drug accountability at sites on an ongoing basis from the start of the study. At the end of the study, it must be possible to reconcile delivery records with records of used and returned study treatments. An account of any discrepancies must be provided. The unblinded monitor will prepare a final report of the accountability of the investigational product for filing in the investigator file.

Nanocort should be stored between 2 and 8°C, protected from light and kept in an appropriate secure area (e.g., a locked cabinet). All other related material can be stored at room temperature or per manufacturer's instructions.

The Sponsor (or designee) can provide the framework for documenting study treatment accountability throughout the study. The Investigational site must maintain an accurate written record of the shipment, dispensing, and return of study treatments. And an accurate

record of the date and amount of study drug dispensed to each subject must be available for inspection at any time.

At the conclusion of the study and after inspection by the unblinded monitor the Investigator will return all drug containers, drug labels, and a copy of the completed drug accountability form to the monitor for transfer to the appropriate parties. Sites may destroy medications locally at an appropriate time point, if previously agreed with the Sponsor.

8.5 Withdrawal of individual subjects

Subjects can leave the study at any time for any reason if they wish to do so without any consequences. The Investigator can decide to withdraw a subject from the study for urgent medical reasons.

Reasons for subjects to be withdrawn from the study include, but are not limited to;

- The subject withdraws consent.
- Violation of eligibility criteria (if the violation is detected prior to drug administration).
- At the Investigator's or MM's discretion to protect subject safety and well-being.
- Subjects may also be discontinued due to the following: change in compliance with inclusion/exclusion criterion that is clinically relevant and affects safety, occurrence of AEs, intake of non-permitted concomitant medication that might affect safety or study assessments/objectives, etc.

Reasons for discontinuation will be recorded.

Once dosing is complete, subsequent violation of the protocol should not be considered grounds for withdrawal. All subjects treated should be followed up for safety evaluation, if at all possible. If withdrawn due to an AE, subjects must be followed until resolution of all their AEs or until the unresolved AEs are judged by the Investigator is stabilized. In all cases, the date the subject is withdrawn from the study and the reason(s) for withdrawal must be recorded on the electronic case report form (eCRF).

In the case of incomplete drug administration, subjects should not be withdrawn from the study, but should undergo all planned follow-up visits.

If a subject is withdrawn from the study for any reason, the Investigator must make every effort to perform the evaluations described for the End of Study/Early Termination Visit at Day 85 (Week 12), as soon as possible but preferably within 30 Days after their last study drug administration. Subjects withdrawn because of adverse experiences will undergo a

physical examination and laboratory tests planned at the follow-up visit (if required). A follow-up of AEs will also be undertaken.

Replacement of individual subjects after withdrawal

No subjects will be replaced. If any of the subjects is withdrawn from the study, the reason for withdrawal will have to be recorded in the case report form (eCRF) for all withdrawn subjects.

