Secondary objectives: Patient Reported Outcomes and an assessment of pharmacokinetic parameters in a subset population from each treatment group.

Study design:

The study is a randomized, double- blind, double dummy, active controlled, parallel, multi-center study in which IV PEGylated Liposomal Prednisolone Sodium Phosphate (Nanocort) will be compared with IM injection of methylprednisolone acetate (Depo-Medrol®) to evaluate efficacy and safety. Each patient will receive an infusion and an IM injection containing either an active treatment or a dummy treatment. Opaque IV lines, sleeved bags and opaque syringes will be used to maintain blinding of either liposomal product or reference product.

All subjects will be provided an informed consent form (ICF) containing information about the study. After fully understanding of the ICF, subjects will voluntarily sign the ICF. Subjects will enter a screening period for up to 14 Days to assess laboratory values and other inclusion/exclusion criteria. Medical history and serious medical conditions as determined by the Principal Investigator (PI) will be reviewed during screening. In addition, the screening period will include a physical examination, blood and urine collection for laboratory assessments, vital signs, electrocardiogram (ECG) and confirmation of RA diagnosis (flare criteria).

Subjects with active RA who meet all eligibility criteria will undergo Baseline visit (Day 1) assessments. At this visit, prior to receiving treatments, subjects will be assessed for baseline parameters and then will be randomized into one of three groups:

- **Nanocort 75 mg** IV infusion and IM saline injection on Day 1 and Day 15
- **Nanocort 150 mg** IV infusion and IM saline injection on Day 1 and Day 15
- **Depo-Medrol® 120 mg** IM injection and IV saline infusion on Day 1 and Day 15

Dosing will occur on Baseline (Day 1) and Week 2 (Day 15). Study visits will occur at Week 1, Week 2, Week 3, Week 4, Week 6, Week 8 and Week 12 / End of Study (EOS) to assess efficacy and safety evaluations as indicated in the Schedule of Assessments. Subjects receiving any treatment dose will be followed till Week 12 for safety if possible.

Study population:

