5.2.2 Prohibited Medications

The following medication use is restricted and/or will exclude the subject from enrolment in this trial:

- Exposure to an experimental treatment or use of investigational product within the past 30 days prior to Screening, or is still within a washout period of a previous clinical trial.
- Last treatment with oral, rectal or injectable (including intra-articular) glucocorticoids (GCs) must be discontinued for at least 8 weeks prior to Screening Visit and may not be taken throughout the duration of the study.
- Previous treatment with IV gamma globulin, plasmapheresis or ProSORBA® column within 3 months prior to screening and during the study.
- Systemic antibiotics and/ or anti-viral medications for treatment of an active infection required at the time of screening.
- Immunizations or vaccinations during the study period.
- Medications that may cause drug-drug interactions with methylprednisolone in opinion of investigator

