8.1.1 Main study parameter/endpoint

The Primary parameter that will be measured is the EULAR response at Week 1 (Day 8).

Primary Endpoint: EULAR responder (moderate and good combined) rate at Week 1 (Day 8)

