8.3 Study procedures

The Schedule of Assessments (Table 2) included in the protocol summarizes the timing of the efficacy and safety measurements.

The Day of the first dose administered to a subject is considered Day 1 for that individual subject. Other study Days are calculated with Day 1 as the reference point. Screening will consist of period up to 2 Weeks (14 Days) and those subjects that are still eligible after the screening visit will be randomized to one of the three treatment groups.

Treatment will be given on Day 1 and Day 15. The patient will be followed up for 12 Weeks or End of Study visit. In the event of early termination, subjects are asked to return for the Week 12 assessments if possible. Otherwise, the subjects are assessed as per Week 12 assessment schedule on the Day of termination. Infusion related reactions will be monitored during the infusion and at the end of infusion.

Physical Examination

A full physical examination should include: General appearance, Skin, Head and Neck, Eyes-Ears-Nose, Throat, Lymph Nodes palpation, Cardiovascular, Lungs & Chest, Abdomen, Musculoskeletal, and Neurological Function. All other body systems should be assessed at the Investigator's discretion. A full physical examination will be done at Screening, Baseline

and End of study. For remaining visits it will be up to the judgement of the Investigator if a full or abbreviated exam is completed.

Vital Signs

Vitals signs will be taken supine (for 5 minutes) and include heart rate, respiratory rate, blood pressure (BP), and temperature. The method of temperature assessment must remain consistent for each individual subject throughout the study.

Subject blood pressure and heart rate will be measured using an automatic device (whenever possible) after the subject has rested (supine) comfortably for 5 min. Vital signs will be measured at the time points specified in the Schedule of Assessments (Table 2).

Weight will be recorded as per Table 2.

Disease Activity Score in 28 Joints (DAS28)

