10.9 Missing Data

The handling of missing data for the clinical endpoints will be discussed in detail in the SAP.

For the primary endpoint EULAR response on Day 8, subjects who withdraw from the study before Day 8, because of insufficient efficacy will be considered as non-responders.

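### Protocol 8.5 and 8.6 do not separate stopping study drug from leaving the study, so Day 8 and Day 15 EULAR outcomes can be lost, possibly selectively

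*Combined protocol and SAP*

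**What the plan says.** **Leaving the study.** Protocol 8.5 lists reasons for withdrawal from the study. Among the grounds on which a subject may be discontinued are adverse events (AEs) and "intake of non-permitted concomitant medication that might affect safety or study assessments/objectives, etc". Under 5.2.2, oral, rectal and injectable glucocorticoids "may not be taken throughout the duration of the study".

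**Two limits on withdrawal.** The first, in 8.5: "Once dosing is complete, subsequent violation of the protocol should not be considered grounds for withdrawal". The second, in 8.5 and again in 8.6: "In the case of incomplete drug administration, subjects should not be withdrawn from the study, but should undergo all planned follow-up visits". The first applies only after the last dose. The second has no time limit. Section 8.6 is headed as follow-up after withdrawal from treatment, but its text is about withdrawal from the study.

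**Follow-up after leaving.** Section 8.3 says: "In the event of early termination, subjects are asked to return for the Week 12 assessments if possible". Sections 8.5 and 8.6 likewise point to the End of Study/Early Termination evaluation.

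**Analysis.** Protocol 10.8 restricts the primary analysis to subjects who had the first dose and whose EULAR response was assessed. Protocol 10.9 adds that "subjects who withdraw from the study before Day 8, because of insufficient efficacy will be considered as non-responders". SAP 4.2 imputes partial AE dates and nothing else, and otherwise uses available data. SAP 4.4.2 does not reassign visits by date.

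**The concern.** The decisive endpoints fall in the first 15 days. That is when 8.5 leaves withdrawal for non-permitted medication open, and AE withdrawal is open throughout. A subject who takes a systemic glucocorticoid in those two weeks may well be a treatment failure. AE withdrawals could also differ by arm: protocol 6.3 reports infusion reactions in about 9.7% of Nanocort patients to date, whereas the control arm's infusion is saline (5.1.2). If such subjects leave before Day 8 or Day 15, they drop out of the responder rates at those visits, and the rates then describe a selected group.

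Sites also have two rules to choose from. A subject who misses the second dose because of an AE can be withdrawn under the list in 8.5, or kept in for all visits under the incomplete-dosing rule in the same section. Whether the Day 15 outcome exists may depend on which sentence the site follows.

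**Working it through.** **1. Timing.**

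| Item | Source | Day |
|---|---|---|
| Doses | Protocol Summary, 5.1 | 1 and 15 |
| Primary endpoint | Protocol 8.1.1 | 8 |
| Key secondary endpoints | Protocol 8.1.2 | 8 and 15 |
| Bar on withdrawal for violations | Protocol 8.5 | after dosing is complete (undefined; naturally Day 15) |

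The bar therefore begins no earlier than the last of these endpoints.

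**2. Can a lost outcome be recovered?**

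- The early-termination visit includes joint counts, DAS28 and EULAR response (8.3.1), but SAP 4.4.2 keeps it in its own visit slot.
- Protocol 10.9 counts a subject as a non-responder only if withdrawal came before Day 8 and was for insufficient efficacy. AE and medication withdrawals are outside it, and it is silent on Day 15.
- SAP 4.2 has no non-responder rule at all, so even the narrow rule in 10.9 is not carried over. SAP 4.11 does not list this as a change from the protocol.
- The per-protocol analysis is no check, because SAP 2.2 names withdrawal before Week 12 as a likely exclusion.

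**3. The plan's own figure.** Protocol 4.4 gives 110 per arm with about 10% drop-out: 110 × 0.90 = 99 evaluable, 99 / 0.90 = 110, and 3 × 110 = 330. This is consistent. The assumed response rates and power are blacked out and cannot be checked.

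**4. Size, on assumptions.** Two arms of n = 110 have the same true Day 8 responder rate p. One arm loses k subjects, all non-responders, and the other loses none. The available-case bias is p·n/(n − k) − p = p·k/(n − k).

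| k | p = 0.5 | p = 0.6 |
|---|---|---|
| 3 | 55/107 = 51.4%, +1.4 points | 66/107 = 61.7%, +1.7 points |
| 6 | 55/104 = 52.9%, +2.9 points | 66/104 = 63.5%, +3.5 points |
| 11 | 55/99 = 55.6%, +5.6 points | 66/99 = 66.7%, +6.7 points |

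If the k = 11 lost subjects were all responders, then at p = 0.5 the rate is (55 − 11)/99 = 44.4%, a bias of −5.6 points. If losses are equal across arms and unrelated to response, the expected bias is zero.

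**5. Effect on one test.** Use a single two-sided comparison at 0.05, normal approximation. This is simpler than the SAP's Hochberg procedure at 0.045. The rejection rate is 1 − Φ((1.96·se0 − d)/se1) + Φ((−1.96·se0 − d)/se1), where d is the bias, se0 the pooled and se1 the unpooled standard error. For p = 0.5 and k = 11: d = 0.0556, se0 = 0.0692, se1 = 0.0690, which gives 0.126. Over p = 0.5 to 0.6 the rate is 0.071 to 0.081 at k = 6 and 0.126 to 0.168 at k = 11.

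**The case against.** Several points on the other side stand, in whole or in part.

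- **AE withdrawals.** A reader might infer that the Day 15 limit also governs them. It does not. The sentence concerns protocol violations only, so AE withdrawal is neither opened nor closed by the end of dosing.
- **Some protection exists before Day 15.** The incomplete-dosing rule already keeps some subjects in, and protocol 6.6 provides for an infusion reaction to be managed and the infusion resumed. So the defect is a conflict between rules. It is not a complete absence of protection.
- **The window for the primary endpoint is narrow.** Withdrawal after the Day 8 visit does not cost the primary outcome. No visit is scheduled between Day 1 and Day 8, and co-medication is asked about at visits (5.2), so forbidden medication would often come to light when DAS28 is being measured anyway. This lowers the risk for Day 8. It does not help Day 15 if the subject is withdrawn at the Day 8 visit.
- **Withdrawal is optional, and more than one reason can be recorded.** A site could record insufficient efficacy, which would bring in 10.9 before Day 8. That makes the outcome depend on how the site words the reason. Section 5.2.4 keeps non-responders who receive other RA medication in the study, but only from Week 2.
- **Selective loss as a fact.** A reader might infer that outcomes are in fact being lost selectively, or that the loss favours Nanocort. The documents give no withdrawal counts by arm, time or reason, so neither inference is supported.
- **The size is an extreme case.** The k = 11 row puts an arm's whole 10% drop-out before the endpoint, makes every lost subject a non-responder, and assumes no loss in the other arm.

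**Conclusion.** The point holds as an internal conflict with a consequence for the data. Sections 8.5 and 8.6 do not distinguish stopping study drug from leaving the study. Their withdrawal list conflicts with their incomplete-dosing rule, and neither document recovers a Day 8 or Day 15 outcome lost to an AE or medication withdrawal. Outcomes can be lost, and the loss may be related to response.

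The illustrated bias is 1.4 to 6.7 points for 3 to 11 lost non-responders in one arm only. It rests on an assumed 110 per arm, an assumed 50-60% responder rate and one-sided loss. Other patterns give no bias or bias of the opposite sign. SAP 4.1 and section 6 report early termination with enrolment below plan, so 110 is not the achieved size. With smaller arms, the same k weighs more. This should be corrected, but it does not show that the results are biased.

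**What to change.** **Protocol.** Reconcile 8.5 and 8.6 with each other and with their incomplete-dosing rule, and use separate terms for stopping study drug and leaving the study. State that subjects dosed at least once keep the already scheduled Day 8 and Day 15 DAS28/EULAR assessments after an AE, non-permitted medication or a protocol violation, unless consent is withdrawn or the investigator judges the visits unsafe. This concerns data collection only. No clinical rule on treatment needs to change.

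**SAP.** Because the study ended early, new protocol wording cannot recover visits already missed, so the SAP change carries most of the remaining value.

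- Reconcile SAP 4.2 with protocol 10.9, and record the result in SAP 4.11.
- Extend the disposition summary in SAP 4.5, which already gives discontinuation reasons by treatment, to show withdrawals before Day 8 and before Day 15 by arm and reason.
- Add an analysis of the primary and key secondary endpoints that counts dosed subjects who withdrew before the relevant visit as non-responders, including those whom the SAP 2.1 requirement for an efficacy measurement after baseline would leave out.
- Specify all of this before unblinding. If that has passed, label the analysis post hoc.

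**Cost.** An amendment and a site letter if any subjects are still being followed, a few extra visits, some data collected under other medication, one table split and one extra analysis.

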8.6 Follow-up of subjects withdrawn from treatment

All subjects treated should be followed up for safety evaluation if at all possible. If withdrawn due to an AE, subjects must be followed until resolution of all their AEs or until the unresolved AEs are judged by the Investigator and MM to have stabilized. In all cases, the date the subject is withdrawn from the study and the reason(s) for withdrawal must be recorded on the case report form (eCRF).

In the case of incomplete drug administration, subjects should not be withdrawn from the study, but should undergo all planned follow-up visits.

If a subject is withdrawn from the study for any reason, the Investigator must make every effort to perform the evaluations described for the End of Study/Early Termination Visit at Day 85 (Week 12), as soon as possible but preferably within 30 Days after their last study drug administration.

8.7 Premature termination of the study

The study may be discontinued at the discretion of the Principal Investigator, Sponsor, or Independent Ethics Committee (IEC) based on the occurrence of the following (but not limited to):

- AEs unknown to date with respect to their nature, severity, and duration;
- Increased frequency and/or severity and/or duration of known AEs;
- Medical or ethical reasons affecting the continued performance of the study;
- Difficulties in recruitment;
- Cancellation of drug development;
- Notification by regulatory authorities

The written information concerning premature termination of the study will be provided to applicable recipients, such as Investigators, Sponsor or IECs.

9. SAFETY REPORTING

9.1 Disadvantageous event

In accordance to applicable legislation and guidelines, the Investigator will inform the subjects and the reviewing accredited ethical committee if anything occurs, on the basis of which it appears that the disadvantages of participation may be significantly greater than was foreseen in the research proposal. The study will be suspended pending further review by the accredited ethical committee, except insofar as suspension would jeopardise the subject's health. The Investigator will take care that all subjects are kept informed.

9.2 AEs, SAEs and SUSARs

9.2.1 Adverse events (AEs)

An adverse event (AE) is any untoward medical occurrence in a subject who has received study drug, or any untoward or unintended response to an experimental intervention which does not necessarily have a causal relationship with the treatment. Adverse Events include:

- Any new undesirable medical experience or an unfavourable and unintended change of an existing condition that occurs during or after treatment.
- Untoward clinically significant manifestations of laboratory abnormalities (e.g., clinical chemistry, haematology, urinalysis, etc.) or other abnormal assessments (e.g., electrocardiogram, vital signs) independent of the underlying medical condition. If possible, abnormal laboratory findings with these characteristics should be reported as a clinical diagnosis rather than the abnormal value itself (e.g., "anemia" rather than "decreased blood count").

Situations where an untoward medical occurrence has not occurred (e.g., hospitalisation for elective surgery, social and/or convenience admissions) do not represent AEs.

Subjects will be carefully monitored throughout the study for AEs. At each study visit, subjects will be asked to report any AE. All AEs are followed until they are resolved or stabilized, or until all attempts to determine resolution of the event are exhausted. The investigator will use his/her discretion in ordering additional tests as necessary to monitor the resolution of such events.

Each collected AE, regardless of the relationship to study drug, will be recorded in the AE eCRF. All entries should contain an event term, date of onset, date of resolution, severity, action taken, outcome, relationship to study drug, and a seriousness assessment. The investigator will document all AEs in the subject's source document.

Severity will be assessed by Investigator according to the following definitions:

Mild: The event is of little concern to the subject and/or of no clinical significance. The event is not expected to have any effect on the subject's health or wellbeing.

Moderate: The subject experienced discomfort enough to cause interference with usual activity, and/or the condition required specific treatment. The event is of some concern to the subject's health or wellbeing. The event may require medical intervention.

Severe: The subject is incapacitated and unable to work or participate in many or all usual activities. The event is of definite concern to the subject and/or poses substantial risk to the subject's health or wellbeing. The event is likely to require medical intervention and/or close follow-up.

Life-threatening: The subject is at risk of death due to the adverse event as it occurred. This does not refer to an event that hypothetically might have caused death if it were more severe.

Death: Death related to adverse event.

Action taken is categorized as "none", "study drug discontinued", "study drug discontinued and restarted", "dose modified", "required concomitant medication", "required procedure", or "other".

Event outcome at resolution, or time last follow-up was recorded is categorized as: "event resolved"; "resolved with sequelae"; "ongoing"; "lost to follow-up"; or "death".

The investigator will determine the relationship of the event to the study drug according to the following criteria:

- **Not related:** The event was most likely caused by other factors such as the subject's clinical condition, intercurrent illness, or concomitant drugs, and did not follow a known response pattern to the study drug, or the temporal relationship of the event to study drug administration made a causal relationship unlikely.
- **Unlikely:** A clinical event, including laboratory test abnormality, with a temporal relationship to drug administration which makes a causal relationship improbable, and in which other drugs, chemicals or underlying disease provide plausible explanations.

- **Possibly related:** The event followed a reasonable temporal sequence from the time of drug administration, and/or followed a known response pattern to the study drug, but could have been produced by other factors such as the subject's clinical condition, intercurrent illness, or concomitant drugs.
- **Probably related:** The event followed a reasonable temporal sequence from the time of drug administration, and/or followed a known response pattern to the study drug, and could not be reasonably explained by other factors such as the subject's clinical condition, intercurrent illness or concomitant drugs.
- **Related:** The event follows a reasonable temporal sequence from administration of the drug; that follows a known or expected response pattern to the suspected drug; that is confirmed by stopping or reducing the dosage of the drug; and that is not explained by any other reasonable hypothesis.

